4.4.2. Intervention group MSK clinician training

We will use our existing networks to identify physiotherapists and chiropractors who are appropriately qualified and interested in delivering the intervention. Clinicians will undergo a training program organised by the research team. This training will cover the intervention

details, requirements for team-based care procedures within a GP primary care model. This training will be conducted face-to-face at Macquarie University campus prior to the commencement of the trial.

4.4.3. Comparison group: usual GP-led care

Usual GP-led care will be provided in the comparison primary care sites. GPs in the comparison group are free to provide the care they would normally provide, including referral to clinicians such as physiotherapists or chiropractors. Interventions provided or recommended by the GP will be recorded and monitored.

4.5. Outcome Measures

Self-reported patient outcome measures will be collected at baseline, 2-weeks, 6 weeks, 3-, 6-, 9-, and 12-months from the initial visit with a primary comparison at 3-months. See the Table for the timing of each of the outcomes. All these outcomes will be collected using REDCap and will be completed by participating patients. If they are unable to enter their information directly, a study RA will assist them to do this over the telephone/Zoom.

See Appendix – Data collection forms for all outcomes that will be used for this study and the data collection time points.

Table: Patient participant outcome measures and timing

Outcome measure	Baseline	2 weeks	6 weeks	3 months (primary comparison)	6 months	9 months	12 months
Individual health outcomes							
Pain intensity questions based on Brief Pain Inventory	X	X	X	X	X	X	X
Roland Morris Questionnaire (RMQ)	X	X	X	X	X	X	X
EQ-5D-5L	X	X	X	X	X	X	X
PSEQ	X	X	X	X	X	X	X
TSK	X	X	X	X	X	X	X
GROC		X	X	X	X	X	X
Patient satisfaction		X	X	X	X	X	X
Adverse events		X	X	X	X	X	X
Health system, societal and cost outcomes							
Healthcare utilisation	X			X	X	X	X
Absenteeism/Presenteeism (iPCQ)	X			X	X	X	X

NB: EQ-5D-5L = European Quality of Life five dimensions: mobility, self-care, usual activities, pain/discomfort and anxiety/depression questionnaire. PSEQ = Patient Self-Efficacy Questionnaire; TSK = Tampa Scale for Kinesiophobia; GROC = global rating of change. iPCQ = Productivity Cost Questionnaire

4.5.1. Primary Outcome Measure:

Self-reported LBP disability using the Roland Morris Questionnaire (RMQ) ¹⁴ measured at 3 months. Disability and function are considered the most important outcomes for people with LBP ¹⁵.

4.5.2. Secondary Outcome Measures:

4.5.2.1. Individual health outcomes:

LBP intensity using the Brief Pain Inventory (BPI) severity index ¹⁶. Health-related quality of life: using the European Quality of life questionnaire EQ-5D-5L ¹⁷, which demonstrates good reliability and validity, and is suitable for economic evaluation in LBP ¹⁸. The utility score will be used to calculate quality-adjusted life years (QALY) for our outcome in the economic evaluation. Global rating of change: using an 11-point global rating of change scale (GROC) (-5 to +5) as has been recommended for self-reported rating of change ¹⁹. The Pain Self-Efficacy Questionnaire (PSEQ) will measure psychosocial factors associated with LBP related disability ²⁰ and The Tampa Scale for Kinesiophobia will quantify fear of movement and reinjury ²¹. Patient satisfaction and experience: using an 11-point scale, extremely dissatisfied (-5) to extremely satisfied (+5). Adverse events: using a self-reported adverse events questionnaire consistent with reporting guidelines (Appendix–AE REPORTING) ²².

4.5.2.2. Health system, societal and cost outcomes

These secondary outcomes will all be self-reported with patients completing the questionnaires using the study REDCap database, measured over 12 months.

GP workload: number of repeat GP visits for LBP.

Healthcare utilisation: using a patient self-reported questionnaire, with total count over 15 months for all types of visits combined, focused on: consultations with health professionals outside the trial (e.g., physiotherapists, chiropractors, massage therapists, specialists), emergency department visits, diagnostic imaging, medications, and other treatment.

Absenteeism/Presenteeism: self-reported time (days) lost from normal activities related to LBP using a modified iPCQ ²³.

Costs: Sources of direct healthcare cost data: Intervention costs will include the MSK clinician salary, training, space, and resources and equipment needed to carry out the intervention. Self-reported costs will be used for private healthcare services and other costs incurred by the participant. MBS/PBS data will be collected to determine medications taken and the healthcare services that are used. This will allow us to complete an economic analysis to determine the cost of health care related to the trial intervention.

Indirect costs: non-healthcare costs will be limited to loss of productivity (LOP) using a human capital approach. The mean Australian wage reported by Australian Bureau of Statistics will be used to assign a monetary value to time lost from paid employment by both patients and caregivers. For retirees, we will determine time lost from volunteer, homemaking, or usual activities, and apply the minimum wage value in New South Wales.

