3. PROJECT AIMS

The overarching goal of this CRT is to evaluate whether integrating a MSK clinician (physiotherapist/chiropractor) within primary care teams for people with LBP and making this clinician available to LBP patients as an early point of contact, will improve outcomes. The specific aims are to determine whether a new model of care for people presenting to primary care with LBP, incorporating a team-based approach, is more effective than usual GP-led care, evaluated over a one-year period, for:

- 1) disability (primary outcome at 3 months), pain intensity, quality of life, global rating of change, patient satisfaction, and adverse events.
- 2) health system and societal outcomes, including healthcare access, GP workload, emergency department visits, diagnostic imaging, opioid medications used, and missed work.
- 3) cost-effectiveness.

Further, a process evaluation will assess the implementation of the model of care and the perspectives of patients and primary care providers towards the model. This current ethics application does not include the process evaluation; we will submit the ethics application for the process evaluation at a later date.

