4.1.3.3 Patient participant selection criteria

Patient inclusion criteria: adults (≥ 18 years) with LBP (with or without associated leg pain) of any duration, who can read, write, and speak in English. We have excluded non-English speaking patients due to the cost burden of employing interpreters at each of the 20 primary care sites. LBP is defined as pain between the 12th rib and the buttock crease.

Patient exclusion criteria: known or suspected serious pathology as the cause of LBP (e.g. cancer, infection or fracture) or neurodegenerative disease, or inability to complete the scheduled follow-ups over 1-year.

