4.8.2. Health outcome data analysis

All analyses will be by intention-to-treat. Our primary outcome (RMQ) with repeated measures at 0, 2-week, 6-weeks, 3-, 6-, 9-, and 12-months will be analysed using linear mixed-effects regression, estimated using restricted maximum likelihood (REML). The model will include fixed effects for time, group by time interaction (omitting the group main effect to ensure baseline differences are constrained to 0), factors used in the covariate constrained allocation procedure, and other prespecified covariates associated with LBP-related disability. The correlation in repeated measures on the same participant will be modelled using a suitable covariance structure, identified using information criteria (AIC/BIC) and likelihood ratio tests. To account for clustering within practices, site will be modelled as a random effect. The intervention effect will be obtained as the adjusted least square mean difference between arms at 12-months together with 95% confidence intervals. Secondary comparisons will be obtained using least square mean differences at intermediate time points. The use of REML estimation under an assumption of missing at random allows the use of all available data without the need for multiple imputation. To examine the risk of bias due to missing data, we will compare characteristics of those remaining and those lost to follow-up to identify factors associated with attrition and adjust for any such factors as covariates. Secondary outcomes (remaining individual health outcomes, healthcare access, GP workload, healthcare utilisation, and lost work) that are continuous will be analysed as described for the primary outcome, while secondary outcomes that are categorical will be analysed using generalised linear mixed effects modelling with binomial, Poisson, or negative binomial distribution. We will analyse results after completion of 12-month follow-up with no planned interim analyses.

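### The missed-work objective is measured by days lost from normal activities, and the indirect-cost rule gives no value to the unpaid time of non-workers who are not retired

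*Protocol*

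**What the plan says.** The Summary and section 3 (Project Aims) list the health-system and societal outcomes of objective 2, ending with "diagnostic imaging, opioid medications used, and missed work". Section 4.8.2 names the secondary outcomes to be analysed as the remaining individual health outcomes and "healthcare access, GP workload, healthcare utilisation, and lost work".

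The outcome is defined once, in 4.5.2.2, under a heading that names both absenteeism and presenteeism: "self-reported time (days) lost from normal activities related to LBP using a modified iPCQ". The table in 4.5 schedules it at baseline and at 3, 6, 9 and 12 months. Patient eligibility (4.1.3.3) is "adults (≥ 18 years) with LBP (with or without associated leg pain) of any duration", subject to English language and the listed exclusions. It contains no employment criterion.

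On indirect costs, 4.5.2.2 says that "non-healthcare costs will be limited to loss of productivity (LOP) using a human capital approach". It then gives two pricing rules. Paid working time lost by patients or caregivers is priced at the national mean wage. For unpaid time: "For retirees, we will determine time lost from volunteer, homemaking, or usual activities, and apply the minimum wage value in New South Wales". Section 4.8.3 makes the societal perspective primary.

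**The concern.** Missed work and days lost from normal activities are different quantities. A retired patient can lose normal-activity days and cannot miss paid work. A worker can lose a weekend of normal activity without missing a shift. If the outcome is analysed as defined, objective 2 is answered on a mixture, and the result cannot be read as an effect on work.

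The pricing rule has a related gap. The endpoint can count days lost by people who are neither in paid work nor retired, but neither pricing rule reaches their own time. Homemaking is priced when a retiree loses it and has no stated price when a non-retired homemaker loses it. This sits in the primary economic perspective, where productivity is the only non-healthcare cost.

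Presenteeism is in the heading, but the stated unit is days lost, which does not describe reduced performance while at work.

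**Working it through.** The protocol gives no numerical figure for this outcome or its cost, so there is nothing to reproduce. The check is a comparison of the texts, followed by an illustration on assumed inputs.

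**Step 1: construct.**

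| Place | What is named |
|---|---|
| Summary; section 3 | missed work |
| 4.8.2 | lost work |
| 4.5 table; 4.5.2.2 heading | absenteeism and presenteeism |
| 4.5.2.2 definition | days lost from normal activities |

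Three of the four rows concern work. The row that defines the variable does not.

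**Step 2: how far the pooled figure can differ from the work effect.** Let *w* be the share of participants in paid work, *D* the days saved per worker and *e* the days saved per non-worker. Assume that a worker's saving in normal-activity days equals the saving in work days. Then

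pooled difference = *w* × *D* + (1 − *w*) × *e*.

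All three inputs are assumptions: *D* = 2, *w* from 0.4 to 0.8, *e* from 0 to 3.

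| *w* | *e* = 0 | *e* = 1 | *e* = 3 |
|---|---|---|---|
| 0.4 | 0.8 | 1.4 | 2.6 |
| 0.6 | 1.2 | 1.6 | 2.4 |
| 0.8 | 1.6 | 1.8 | 2.2 |

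For example, 0.4 × 2 + 0.6 × 0 = 0.8, and 0.4 × 2 + 0.6 × 3 = 2.6. The pooled difference equals the worker effect of 2 days only when *e* = *D*. It lies below 2 when non-workers gain less than workers and above 2 when they gain more.

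**Step 3: coverage of the pricing rules.**

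| Participant | Own time lost | Stated price |
|---|---|---|
| In paid work | paid time | national mean wage |
| Retired | volunteer, homemaking or usual activities | NSW minimum wage |
| Non-retired homemaker, student, carer or unemployed | the same kinds of unpaid time | none stated |

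If a share *u* of participants falls in the last row and loses days at the average rate, a share *u* of all lost days has no price. For an assumed *u* of 5% to 30%, that is 5% to 30% of lost days. Paid time lost by a caregiver of such a participant would still be priced. The protocol gives neither employment shares nor wage values, so no money amount can be derived.

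**The case against.** The strongest reply is that scoring rules, the analysis set for a work outcome and detailed unit costs usually belong in a statistical or health-economics plan, which may exist and is not shown. That would answer a complaint about silence. Here, however, the protocol has itself fixed the definition of the variable and the groups whose unpaid time is priced. A later plan that follows this text inherits the mismatch.

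Three stronger readings are tempting, and the document does not support them.

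- *Presenteeism is collected but never scored or costed.* The limit stated in 4.5.2.2 is loss of productivity, which can include reduced output at work. The modified iPCQ form is in an appendix that is not shown. What stands is narrower: neither the stated days-lost unit nor the stated pricing describes impaired work.
- *Pooling must dilute the effect on work.* Suppose 60% of participants work and lose 6 v 4 days, while the other 40% lose 10 days in both arms. The pooled means are 0.6 × 6 + 0.4 × 10 = 7.6 and 0.6 × 4 + 0.4 × 10 = 6.4, a 16% reduction against 33% in workers. That result comes from assuming no benefit in non-workers. If they also improve by a third (10 to 6.67), the pooled means are 7.6 and 0.6 × 4 + 0.4 × 6.67 = 5.07, again a 33% reduction.
- *The plan sets the time of other non-workers at zero.* It does not say so. They are a missing category, and zero is what follows if the two written rules are applied and nothing is added.

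It is also fair to say that the analysis population for this outcome is not stated. That non-workers contribute is an inference from the absence of a restriction, though it is the natural reading. Finally, chance differences in employment mix between arms affect any productivity cost, and a gap between mean and minimum wage would remain after the fix.

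**Conclusion.** The point holds on two counts. First, the defined endpoint does not measure the missed work named in objective 2 and 4.8.2, and the sections must be reconciled. The size and direction of the discrepancy are unknown. On the assumed inputs, a 2-day effect in workers appears as 0.8 to 2.6 days in the pooled outcome, so a reader should not infer that it is necessarily halved or diluted. Second, the pricing rules as written leave out the unpaid time of participants who are neither in paid work nor retired. The share of lost days affected equals their share of participants if they lose days at the average rate.

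On presenteeism, the conclusion is only that its use needs to be stated. The point concerns a secondary outcome and the economic evaluation. The primary RMQ comparison is not touched.

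**What to change.** In 4.5.2.2:

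1. Define missed work as days absent from paid work because of LBP, among participants in paid work at baseline. Use the same term in the aims and in 4.8.2.
2. Report days lost from unpaid or usual activities as a separate outcome in all participants.
3. In the indirect-cost rule, replace the restriction to retirees with all participants not in paid employment.
4. State how presenteeism items from the modified iPCQ enter the outcome and the loss-of-productivity cost. If the form has no such items, remove presenteeism from the heading and from the table in 4.5.

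The questionnaire is already scheduled at baseline and at 3, 6, 9 and 12 months, so no extra visit is needed. The change is one of wording, provided that the form, which is not shown, separates paid work from other activities and records employment status. The downside is small: the missed-work outcome uses fewer participants, so its estimate will be less precise.

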4.1.1. General practitioner participant recruitment

Planned recruitment is 20 primary care sites across Australia, with at least 2 GPs from each site who are willing to participate. We will recruit GPs within these primary care sites by the following methods:

- 1) **Advertising:** we will place advertisements in primary health network (PHN) newsletters across Australia. We will use the internet to advertise on websites such as the Royal Australian College of General Practitioners (RACGP) or similar, and on social media platforms such as Facebook in order to target GPs who may be interested in participating in the research (Appendix–ADV). We will also run information sessions face to face or online where we will discuss the trial for GPs who are potentially interested in the study.
- 2) **Direct contact:** If one of the research team or our PHN collaborators has a professional contact within a GP practice they will make initial direct contact (phone, email or face to face) to inform the practice about the potential study, provide the PICF, and determine their interest in participating in the study. We may also contact other GP practices where we do not have professional contacts, via email or phone call.

After initial contact, GPs who are interested in finding out more will be provided with a PICF and any questions they have will be answered by the research team before GPs consent to take part in the project. GPs will be screened by an RA for inclusion/exclusion criteria.

A flow chart outlining the precise method of communication and informed consent procedure is outlined in the appendix section, primary care site Consent Flow chart (Appendix–FLOW).

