4.8.3. Economic data analysis

We will perform our economic evaluation (cost utility analysis) from both societal (primary) and patient/consumer (secondary) perspectives to meet the needs of key stakeholders. The total costs will be determined by multiplying the quantity of resource use by the corresponding unit cost, summing the total cost over each follow up interval, and then calculating the mean cost at each follow-up time point, as well as an overall mean cost for the entire study period. Results will be presented as aggregated and disaggregated costs. To allow for the correlation between costs and outcomes, recognise clustering, and accommodate the hierarchical structure of the data, we will use bivariate multilevel modelling to estimate the incremental cost-per-QALY gained. We will present the uncertainty surrounding our estimate using bootstrap resampling to construct a cost effectiveness ellipse and cost-effectiveness acceptability curves.

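### Costing retirees' lost usual activities goes beyond the stated productivity limit and risks counting that loss in both costs and QALYs; separately, the price is a single-state wage

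*Protocol*

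**What the plan says.** Under indirect costs, Protocol section 4.5.2.2 sets a limit: "non-healthcare costs will be limited to loss of productivity (LOP) using a human capital approach". It then gives two valuation rules. For paid work, of patients and of caregivers, "The mean Australian wage reported by Australian Bureau of Statistics will be used to assign a monetary value to time lost from paid employment". For retirees, "we will determine time lost from volunteer, homemaking, or usual activities, and apply the minimum wage value in New South Wales". The instrument for lost time is described in the same section as "self-reported time (days) lost from normal activities related to LBP using a modified iPCQ".

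On the effect side, the note to the outcome table in section 4.5 spells out the EQ-5D-5L as "European Quality of Life five dimensions: mobility, self-care, usual activities, pain/discomfort and anxiety/depression questionnaire". Section 4.5.2.1 says that the utility score from this instrument will be used to calculate QALYs for the economic evaluation.

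Section 4.8.3 brings the two sides together. The societal perspective is primary and the patient/consumer perspective secondary, and "we will use bivariate multilevel modelling to estimate the incremental cost-per-QALY gained". On geography, section 4.1.1 states: "Planned recruitment is 20 primary care sites across Australia".

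**The concern.** The retiree rule is wider than the limit two sentences before it. Volunteering and homemaking can be read as unpaid production. The remaining usual activities of a retired person, such as leisure, social life and self-directed daily routine, are not evidently production, yet as worded they would be costed.

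The same domain is scored in the EQ-5D-5L. A retiree who cannot carry out usual activities may lose utility, and so QALYs, and may also generate a cost for the days lost. If the model of care restores those activities, cost falls and QALYs rise for what may be one and the same benefit. If the model does worse than usual care, it is penalised on both sides. Either way the incremental cost per QALY is pushed further in the direction of the clinical effect.

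The matter is relevant because cost-effectiveness is the third specific aim, adults are eligible with no upper age limit, and disability is the primary outcome, so daily function is what the model is meant to change. Section 4.5.2.2 states this valuation for retirees only.

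The single-state price is a different and smaller matter: two unit-cost sources with different geographic scope are used within one cost component of a national trial.

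**Working it through.** There is no figure in the protocol to reproduce: it gives no retired share, days lost, hourly wage or expected QALY gain. The check is therefore a tracing of one item through both sides of the ratio, followed by an illustration on assumed inputs.

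**Tracing the item**

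1. *Cost side.* Section 4.5.2.2 limits non-healthcare costs to productivity, then lists three kinds of retiree time: volunteering, homemaking and usual activities. The third is open-ended. Nothing in the section restricts it to productive time.
2. *Effect side.* Usual activities are one of the five EQ-5D-5L dimensions (section 4.5, table note), and the utility score becomes the QALY (section 4.5.2.1).
3. *Same follow-up.* The outcome table collects the EQ-5D-5L at baseline, 2 weeks, 6 weeks and 3, 6, 9 and 12 months, and the iPCQ at baseline and 3, 6, 9 and 12 months. Both cover the same year.
4. *Same ratio.* Section 4.8.3 combines the costs and QALYs in one incremental estimate.
5. *Safeguard.* No section separates retirees' productive unpaid time from their other usual activities, or says how overlap with the QALY is avoided. The bivariate model is there to allow for the correlation between costs and outcomes and for clustering. It does not remove an item that contributes to both means.

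**Illustration (every input is an assumption)**

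- Retired share of participants, s: 0.10 to 0.40
- Days of activity regained per retiree, d: 1 to 10
- Hours per day: 7.6
- Hourly wage, w: AUD 20 to 25
- QALY gain, ΔQ: 0.02, with 0.01 and 0.05 as alternatives

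Cost offset per participant = s × d × 7.6 × w

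- Low: 0.10 × 1 × 7.6 × 20 = AUD 15.2
- High: 0.40 × 10 × 7.6 × 25 = AUD 760

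Shift in cost per QALY = offset / ΔQ

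| ΔQ | Low (AUD per QALY) | High (AUD per QALY) |
|---|---|---|
| 0.01 | 15.2 / 0.01 = 1,520 | 760 / 0.01 = 76,000 |
| 0.02 | 15.2 / 0.02 = 760 | 760 / 0.02 = 38,000 |
| 0.05 | 15.2 / 0.05 = 304 | 760 / 0.05 = 15,200 |

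These figures price all of retirees' costed days, including volunteering and homemaking, which would rightly stay in. The overlap is only the non-productive part. If that part were one quarter (again an assumption), the offset would be 0.25 × 15.2 = AUD 3.8 to 0.25 × 760 = AUD 190 per participant. At ΔQ = 0.02 this is AUD 190 to 9,500 per QALY.

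**The wage**

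Paid time is priced from a national mean and retirees' time from a New South Wales minimum, while sites are recruited across Australia. The documents give neither figure, so the size of any difference from a national minimum cannot be calculated.

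**The case against.** The strongest reply is that double counting is inferred from a shared phrase. The iPCQ records days; the EQ-5D-5L yields a utility. How much of the costed time the utility already reflects depends on the wording of the modified iPCQ items and on the value set, and neither is shown. This stands. A reader might infer that any change in retirees' daily function is certainly counted twice, but the documents support only a risk, confined to usual activities that are not productive.

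Second, the retiree sentence can be read under the section's own productivity limit, so that all three kinds of time mean unpaid production. That is a possible reading. If it is the intended one, deleting the open-ended term loses nothing.

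Third, the dividing line is not drawn by the EQ-5D-5L description. The protocol gives only the dimension's name, and homemaking might also fall within it, so some overlap could remain after the change. This too stands. The line proposed here follows the protocol's own limit to productivity, and costing unpaid work is a legitimate choice under a societal perspective.

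Fourth, section 4.8.3 promises aggregated and disaggregated costs and a second perspective. That helps a reader weigh the productivity component, but no separate retiree line is promised and the item stays in the primary estimate. Nor is this simply detail left to an analysis plan: the protocol already fixes what is costed and at what price.

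Finally, a reader might infer that the New South Wales wage contributes to the double counting. It does not. A unit price cannot put an item on both sides of the ratio. The rule already applies one value to all retirees, and nothing in the documents shows that this value differs from a national one.

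**Conclusion.** The concern holds as a risk. Section 4.5.2.2 costs an item for retirees that goes beyond its own limit to lost productivity and that shares a named domain with the instrument behind the QALY. Retirees' non-productive usual activities may therefore be counted in both costs and effects of the primary societal analysis, in the same direction.

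The size cannot be determined from the protocol. The illustrative range is wide, rests wholly on assumed inputs, and is an upper bound for each set of inputs because it includes time that should remain costed. No central value should be taken from it; the effect could be negligible or material. It concerns one cost item in one subgroup of the economic evaluation and does not touch the primary clinical outcome, the power or safety. It is worth changing because the change is cheap and is best made before cost results are seen.

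The state wage is a separate and minor inconsistency in the source of unit costs, with no demonstrated bias.

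**What to change.** In section 4.5.2.2, delete *or usual activities* from the retiree rule for the base case, so that only time lost from unpaid productive work (volunteering and homemaking) is costed. If the broader valuation is wanted, present it as a sensitivity analysis alongside the base case. Check that the modified iPCQ lets retirees report volunteering and homemaking time separately from other activities; if it does not, split the item.

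Separately, replace the New South Wales minimum wage with one national minimum wage value for all sites, in line with the national source already used for paid time.

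The cost is a wording change, possibly one split questionnaire item, and a slightly smaller productivity component. If data have already been collected on an unsplit item, the separation may not be possible for those participants, and the report should say how their time was handled.
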